1.1 Abstracts

**Study title:**

Surgical strategies after neoadjuvant or induction chemoimmunotherapy in operable small cell lung cancer

**Research Brief:**

Lung cancer is one of the most common malignant tumors worldwide and has the highest mortality rate among malignant tumors. In recent years, with the gradual development of therapeutic modalities such as targeted therapy and immunotherapy, the overall survival of lung cancer patients have improved significantly. However, late tumor staging at the time of diagnosis often leaves patients with only pneumonectomy, which affects the prognosis with a higher rate of postoperative complications than lobectomy, poorer quality of life, and the possible loss of the opportunity to continue adjuvant therapy.

Our group proposes to conduct this single-arm prospective clinical study to investigate the feasibility, safety, and prognosis of the conversion from pneumonectomy to lobectomy after neoadjuvant or induction therapy in patients with operable non-small cell lung cancer.

**Study Objective :**

Primary objective: to investigate the feasibility of switching to lobectomy after neoadjuvant/induced chemoimmunotherapy in patients with operable non-small cell lung cancer requiring pneumonectomy at first diagnosis (R0 resection rate of lobectomy).

Secondary objective: to investigate the perioperative and long-term outcomes of patients with operable non-small cell lung cancer who were evaluated to undergo pneumonectomy at first diagnosis and switched to neoadjuvant or induction chemoimmunotherapy and subsequent lobectomy.

**Study population:**

50 cases

- 1) Patients voluntarily participated in this study, had good compliance, could cooperate with the trial requirements to complete observation and follow-up, and signed the informed consent form;
- 2) Be over 18 and under 75 years of age, and is open to both men and women;
- 3) Pathologically confirmed non-small cell lung cancer and clinical stage T2-4N0-2, potentially need pneumonectomy, neoadjuvant, or induction Chemo-immunotherapy
- 4) ASA rating: I-III.
- 5) Cardiac function assessment was adequate for radical lung cancer surgery with normal liver and kidney function.

**Study unit/location :**

This is a multicenter study with 4 centers proposed to participate in.

**Study interventions :**

[figure not shown]
Patients enrolled will further undergo relevant examinations (including chest enhancement CT, PET-CT (optional), cranial MR, bronchoscopy, cardiac ultrasound, pulmonary function, electrocardiogram, and blood tests) and be checked for contraindications to surgery, then be evaluated whether be

amenable to surgical treatment after multidisciplinary discussion (Department of thoracic surgery, department of respiratory medicine, department of radiology). Open or minimally invasive radical lung cancer surgery and systematic lymph node dissection will be performed on eligible patients. The perioperative complications, lymph node dissection, R0 clearance rate, 3-year event-free survival rate, overall and disease-free survival time, quality of life, and pulmonary function will be recorded and analyzed.

**Study duration :** 5 years

**Duration of subject participation : 3 years**

### 1.2 Technology roadmap

## 2. Background of the Study

### 2.1 Significance of the study

Lung cancer is one of the most common malignant tumors worldwide, and the number of new lung cancer cases is expected to be as high as 1.8 million worldwide in 2019 [1]. The mortality rate of lung cancer is the highest among malignant tumors, and one-fifth of all malignant tumor deaths worldwide are due to lung cancer [1].

In recent years, lobectomy is no longer the only option for some early-stage lung cancer patients. Sub-lobe resection can achieve better protection of lung function with the same prognosis. Meanwhile, with the gradual development of targeted therapy, immunotherapy and other treatment modalities, more patients benefit from preoperative tumor downstaging. However, pneumonectomy is still preferred as the first choice for operable patients with tumors invading the main pulmonary artery and main bronchus, even achieving tumor downstaging after neoadjuvant therapy. Pneumonectomy is often associated with higher rates of perioperative complications and mortality than lobectomy, and a higher proportion of patients undergoing total pneumonectomy are lost to postoperative adjuvant therapy, which may have an impact on long-term survival. There is currently no evidence to support the decision to convert to lobectomy in this population.

We propose to conduct a single-arm prospective clinical study to investigate the feasibility, safety, perioperative and long-term outcomes of surgery (converting to lobectomy of pneumonectomy) in patients with locally progressive operable non-small cell lung cancer after neoadjuvant therapy.

### 2.2 Background

For operable early lung cancer, sub-lobe resection has been demonstrated to achieve similar oncologic outcomes compared with lobectomy [2, 3], while preserving the lung function. Pneumonectomy remains the standard surgical procedure for patients whose surgical strategies are pneumonectomy initially, although tumor downstaging after neoadjuvant therapy. More evidence is needed to determine whether the extent of surgical resection can be reduced for these patients.

Although pneumonectomy ensures a good R0 clearance rate, it is associated with a higher rate of perioperative complications and mortality than lobectomy. 355 patients with pneumonectomy were retrospectively analyzed by Gregory D. Jones' team [4], and the mortality rates were 3.7%, 4.5%, and 6.8% at in-hospital, 30 days, and 90 days, respectively, for non-oncological causes. 30- and 90-day readmission rates were 13% and 19%, respectively. The rate of readmission within 30 and 90 days was 13% versus 19%, with cardiopulmonary complications being the most common cause. In retrospective studies [5-8], the 30-day complication and mortality rates for total lung resection were 30% and 5%-8%, compared with 4%-10% and 0%-3% for lobectomy. In addition, the 90-day mortality rate after total lung resection can be 1-2 times higher than the 30-day mortality rate [9-10]. A controlled study published in the Annals of Surgery in 2022 [11] compared postoperative

complications and mortality rates between pneumonectomy and lobectomy by propensity score matching, and showed that the complication rates of grade III or higher and mortality at 90 days were significantly higher in the group of pneumonectomy than lobectomy (21% vs. 13% and 6.9% vs. 1.9%, respectively). The three complications with the highest rates were hypoxic respiratory failure, bronchopleural fistula, and intrathoracic hemorrhage. In addition, cardiovascular complications were significantly higher in the pneumonectomy group.

Marc Riquet's team [12] retrospectively analyzed the 10-year survival of 1466 patients undergoing pneumonectomy, and the 5-year and 10-year survival rates were 32% and 19%, respectively. In the analysis of risk factors affecting long-term survival, the investigators found that patients' general physical status and tumor biology were closely related to prognosis, and that the occurrence of nonfatal postoperative complications independently increased the long-term risk of death, which was considered to be indicative of the fragility of patients' general physical status. The investigators compared the long-term survival of patients in the lobectomy versus pneumonectomy groups using propensity score analysis. Cumulative nonneoplastic mortality at 2 years was twice as high in the pneumonectomy group as in the lobectomy group (21% versus 11%), and cumulative nonneoplastic mortality at 5 years was 24% versus 13% in the pneumonectomy group and 2% in the lobectomy group, with the risk of nonneoplastic death increasing by 9% in pneumonectomy group versus 2% in lobectomy group over the postoperative period. The risk of non-tumor death increased by 9% in the total pneumonectomy group and by 2% in the lobular group at 1-2 years. The most common causes of death in both groups were pneumonia and myocardial infarction, both of which were significantly higher in the pneumonectomy group. These non-oncologic deaths are attributable to the impaired general health status of patients after pneumonectomy. A prospective controlled cohort study by Ulrik Sartipy's team [13] found that patients in the pneumonectomy group had a more pronounced decrease in strength scores than those in the lobectomy group (-32% vs. -17%). Recovery from this decline in strength scores was different between the two groups, with Bram Balduyck's team [14] finding that strength scores in patients who underwent lobectomy returned to baseline levels within 1 month after surgery, which supports the idea that adjuvant therapy is often initiated in the first month after surgery, whereas in patients who underwent pneumonectomy, strength scores did not return to baseline levels after 1 year of follow-up. The physical strength scores did not return to baseline after 1 year of follow-up. Patients with pneumonectomy were more likely to have dyspnea, pain, and shoulder dyskinesia than those with lobectomy. Because of the decline in general physical status and strength scores, a significant proportion of patients undergoing pneumonectomy did not receive postoperative adjuvant therapy. In the study by Filippo Lococ's team [15], nearly half of the patients did not receive postoperative adjuvant therapy, although the benefit of postoperative adjuvant chemotherapy on long-term survival has been demonstrated in clinical studies [16]. Recent advances in neoadjuvant/adjuvant combination of immuno- and chemotherapy [17] have

increased the rate of long-term survival benefit in patients with operable lung cancer, whereas the loss of access to adjuvant therapy in pneumonectomy patients potentially compromises their long-term survival benefit.

According to the existing clinical studies, patients after pneumonectomy face higher perioperative complications and mortality, and their long-term survival is impaired due to the loss of adjuvant therapy or non-tumor factors, and their quality of life scores are also lower. Taking into account the high efficiency and downstaging rate of neoadjuvant therapy for lung cancer, strict patient screening was performed to reduce surgical trauma while ensuring R0 resection (from pneumonectomy to lobectomy/sleeve lobectomy after neoadjuvant therapy). Reduce perioperative complications and mortality in this population and increase the proportion of postoperative adjuvant therapy for potential long-term survival benefits and improved quality of life. Prospective evidence is lacking. Therefore, our group would like to conduct this single-arm prospective clinical study to explore the safety, feasibility, and long-term outcome of reducing the scope of surgery after neoadjuvant therapy for locally progressive NSCLC, in order to lay the foundation for further research and clinical application.

### 2.3 Expected results of the research

- 1) Expected to publish 2-3 papers in SCI/EI indexed journals.
- 2) Expected to participate in international academic conferences 1-2 times, national

conferences 3-4 times.

## **2.4 Risk/benefit assessment**

### **2.4.1 Known potential risks**

Radical lung cancer surgery is a widely practiced treatment for early stage lung cancer, including pneumonectomy, double lobectomy, sleeve lobectomy and lobectomy or segmental resection, etc. The common potential risks are perioperative complications, including intraoperative or postoperative bleeding, persistent air leakage, lung infections, pleural effusions, and an increase in the rate of local recurrence.

### **2.4.2 Known Potential Benefits**

Narrowing surgical resection in cases that do well on neoadjuvant or induced chemoimmunotherapy preserves lung function, potentially reducing the risk of perioperative complications, and death. It protects the patient's general state of health, reduces the incidence of long-term non-tumor deaths, maintains a high physical strength score, facilitates adjuvant therapy follow-up, and may result in a long-term survival benefit for the patient.

### **2.4.2 Assessment of potential risks/benefits**

It has been shown in retrospective studies that total pneumonectomy is only performed when lobectomy is difficult to achieve R0 resection and is associated with higher perioperative complications and mortality than lobectomy, with a significant impact on the patient's general state of health and strength scores, which may contribute to impaired long-term survival. In patients who do well on neoadjuvant or induction therapy, conversion to lobectomy can potentially reduce the incidence of perioperative adverse events, reduce the risk of immediate and long-term non-tumor death, protect the patient's general health and strength scores, and increase the patient's chances of receiving postoperative adjuvant therapy, thereby reducing the risk of tumor-related death.

Risk-minimizing measures: Select patients with good results of neoadjuvant or induction therapy according to strict admission criteria, review the tracheoscopic biopsy before surgery to clarify the status of the bronchus to be preserved, take frozen pathology to clarify the status of the nearest incision margins during the surgery to decide the actual surgical method, and maintain adjuvant therapy after the surgery to minimize the possibility of increasing the risk of local recurrence. Postoperatively, the patient's vital signs, drainage, and air leakage were closely observed to ensure perioperative safety.

Preoperative and intraoperative reassessment

1 Bronchoscopic biopsy of bronchial mucosa to be preserved/EBUS to assess the condition of the outer wall of the preserved bronchus.

2 In cases of main pulmonary artery invasion prior to neoadjuvant therapy, intraoperative

freezing is performed to assess the status of the arterial wall at the site of original invasion.

3 For cases with transverse fissure invasion, pulmonary fissure margins were frozen for pathologic evaluation.

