### 4. Aims of the study

Primary objective: to investigate the feasibility of conversion to lobectomy after neoadjuvant/induced chemoimmunotherapy in patients with operable non-small cell lung

cancer who are required to undergo pneumonectomy at first diagnosis (R0 resection rate).

Secondary objective: to investigate the perioperative and long-term outcomes of patients with operable non-small cell lung cancer who were evaluated to undergo pneumonectomy at first diagnosis and switched to neoadjuvant or induction chemoimmunotherapy and subsequent lobectomy.

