## 5. Research design

### 5.1 Overall design

In this single-arm, open-label, multicenter, prospective clinical trial, 50 cases of operable non-small-cell lung cancer requiring pneumonectomy were proposed to be enrolled. Patients will be treated with neoadjuvant or inductive combination therapy of immuno- and chemo- by evaluation from multidisciplinary discussion (Department of Thoracic Surgery, department of Respiratory Medicine, department of Radiology), than undergo open or minimally invasive radical surgery for lung cancer and systematic lymph node dissection. Peri-operative complications, lymph node dissection, R0 resection rate, and postoperative short-term and long-term efficacy outcomes will be recorded and evaluated.

Participating centers:

- 1 Ruijin Hospital, Shanghai Jiao Tong University School of Medicine, Shanghai, China
- 2 Shanghai General Hospital of Shanghai Jiao Tong University School of Medicine
- 3 The Ninth People's Hospital of Shanghai Jiao Tong University School of Medicine
- 4 Huadong Hospital, Fudan University Medical College, Shanghai, China

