## **6 Study population**

### **6.1 Inclusion criteria**

The study subjects should meet the following criteria:

- 1) The patients voluntarily participate in the study, have good compliance, can cooperate with the requirements of the experiment to complete the observation and follow-up, and sign the informed consent form.
- 2) Aged over 18 years old, under 75 years old; male and female are not limited;
- 3) Pathologically confirmed non-small cell lung cancer with clinical stage T2-4N0-2, resectable non-small cell lung cancer, potentially needing pneumonectomy and receiving neoadjuvant or induction therapy.
- 4) ASA score: Grade I-III;
- 5) The cardiopulmonary function evaluation can meet the requirements for radical lung cancer surgery, and the liver and kidney functions are normal.

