### **6.2 Exclusion Criteria**

Subjects meeting any of the following criteria will be excluded from this study;

- 1) Those with serious cardiac, pulmonary, hepatic, and renal dysfunctions, unable to tolerate the surgery;
- 2) Those with uncontrollable neurological or psychiatric diseases or mental disorders, poor compliance, and being unable to cooperate and describe the treatment response.
- 3) Those who are going to undergo emergency surgery or palliative surgery due to lung

abscess or hemoptysis.

- 4) Those who have been treated, or are undergoing neoadjuvant or induction radiotherapy or targeted therapy.
- 5) Those who have a combined history of other malignant tumors
- 6) Those who have a history of thoracic surgery
- 7) Those who are pregnant or breastfeeding women
- 8) Patients of childbearing age who refuse to use contraception.

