## **7. Research interventions**

### **7.1 Giving the research intervention**

#### **7.1.1 Description of the research intervention**

After the patients were enrolled in the group, further relevant examinations (bronchoscopy, chest enhanced CT, PET-CT (optional), cranial MR, cardiac ultrasound, pulmonary function, electrocardiogram, and blood test) were completed, contraindications to surgery were ruled out, and they were evaluated to receive neoadjuvant/induced chemo-immunotherapy after multidisciplinary discussion (thoracic surgery, respiratory medicine, pathology). After completion of treatment, the patient is reassessed and discussed multidisciplinary for surgical feasibility. Open or minimally invasive (thoracoscopic-assisted, robotic-assisted) radical lung cancer surgery with systemic lymph node dissection is performed, including

pneumonectomy, lobectomy, combined lobectomy, and sleeve lobectomy (with or without pulmonary angioplasty/sleeve). Based on the surgical pathology and guidelines, the postoperative adjuvant treatment and follow-up plan was individualized after multidisciplinary discussion.

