## **9. Evaluation of study outcomes**

### **9.1 Evaluation of primary and secondary outcomes**

#### Primary Study Endpoints

R0 Resection rate (lobectomy): the proportion of patients with complete tumor removal by lobectomy, as evaluated by the pathologic findings of postoperative lung cancer specimens;

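### The protocol does not fix whether patients enter before chemoimmunotherapy or after a good response to it, so known responders can be enrolled and raise the R0-lobectomy rate

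*Protocol*

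**What the plan says.** Two sections describe enrolment before therapy.

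- Section 5.1 enrols operable patients requiring pneumonectomy and continues: "Patients will be treated with neoadjuvant or inductive combination therapy of immuno- and chemo- by evaluation from multidisciplinary discussion". Surgery follows.
- Section 7.1.1 says of patients already enrolled and worked up that "they were evaluated to receive neoadjuvant/induced chemo-immunotherapy after multidisciplinary discussion". After treatment they are reassessed for surgery.

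The objectives (1.1 and section 4) match this order, because they define the population by the need for pneumonectomy at first diagnosis.

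Section 2.4.2 (Assessment of potential risks/benefits) reads differently. Its first risk-minimising measure is "Select patients with good results of neoadjuvant or induction therapy according to strict admission criteria".

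The eligibility criteria say the following.

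- Section 6.1 item 3: "potentially needing pneumonectomy and receiving neoadjuvant or induction therapy". The synopsis version in 1.1 lists the therapy among the things a patient may need.
- Section 6.2 item 4 excludes "Those who have been treated, or are undergoing neoadjuvant or induction radiotherapy or targeted therapy". Chemotherapy and immunotherapy are not named.
- No criterion in section 6 mentions response.

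The primary endpoint in section 9.1 is "the proportion of patients with complete tumor removal by lobectomy", judged on the surgical specimen. Which patients form the denominator is not stated. Section 8.2 replaces consented subjects who did not receive the study intervention, and it lists disease progression among the grounds for withdrawal.

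**The concern.** The question the trial asks is how often a patient who needs pneumonectomy at diagnosis ends up, after chemoimmunotherapy, with a complete resection by lobectomy. That rate has to count the patients who do not respond, who progress, or who never reach surgery. If a site may enrol a patient after the response is known, those unfavourable outcomes have been filtered out before the count begins, and for that patient the rate describes selected responders.

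In a single-arm trial without a comparator, the primary rate is the main result and nothing else in the design would reveal the selection. An analysis plan could not repair it either, because patients who were never enrolled cannot be added back.

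**Working it through.** **Step 1. What each place implies about the entry point.**

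| Place in the protocol | Implied entry point |
|---|---|
| Objectives (1.1, section 4) | First diagnosis, before therapy |
| 5.1 | Before therapy |
| 7.1.1 | Before therapy |
| 1.1, inclusion 3 | Favours before therapy (therapy is needed) |
| 6.1 item 3 | Open: planned, ongoing or already given |
| 6.2 item 4 | Open: silent on chemotherapy and immunotherapy |
| 2.4.2 | After therapy, if read as admission to the study |

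The synopsis text on interventions takes enrolled patients from work-up and a multidisciplinary discussion to surgery ("Open or minimally invasive radical lung cancer surgery and systematic lymph node dissection will be performed on eligible patients"), and the schedule in 7.5 runs from screening to the peri-operative period. Both would fit late entry, but I give them little weight. A figure that accompanies the synopsis text is not available, and the schedule table is damaged in extraction.

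**Step 2. Can a known responder be enrolled under section 6?** Take a patient who has finished chemoimmunotherapy and responded well. Inclusion 3 can be read to cover this patient, exclusion 4 as worded does not clearly bar the patient, and no other criterion addresses the timing of therapy. Entry is therefore possible by silence, although nothing expressly permits it.

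**Step 3. Direction of the bias.** Let r be the response rate, and let c1 and c0 be the rates of R0 lobectomy in responders and non-responders. Let f be the share of entrants who are already known responders. Count all enrolled patients in the denominator.

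- Rate from first diagnosis: t = r·c1 + (1 − r)·c0
- Rate observed: (1 − f)·t + f·c1
- Excess: f·(c1 − t) = f·(1 − r)·(c1 − c0)

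The excess is positive whenever f > 0, r < 1 and c1 > c0. The last condition is the protocol's own premise: section 2.4.2 offers the smaller resection to patients who do well on therapy.

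**Step 4. Illustration on assumed values.** The documents give none of r, c1, c0 or f. I take r from 0.4 to 0.7 and (c1, c0) = (0.8, 0.1) or (0.9, 0.2). The example column uses r = 0.5, c1 = 0.8, c0 = 0.1, so t = 0.5 × 0.8 + 0.5 × 0.1 = 0.45.

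| f | Example | Range of observed rate | Range of excess (points) |
|---|---|---|---|
| 0 | 45% | 38% to 69% | 0 |
| 0.25 | 0.75 × 0.45 + 0.25 × 0.8 = 53.75% | 48.5% to 74.25% | 5.25 to 10.5 |
| 0.5 | 0.5 × 0.45 + 0.5 × 0.8 = 62.5% | 59% to 79.5% | 10.5 to 21 |
| 1 | 80% | 80% to 90% | 21 to 42 |

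In both pairs c1 − c0 = 0.7, so the excess at f = 1 is 0.7 × (1 − r): 0.7 × 0.3 = 21 points up to 0.7 × 0.6 = 42 points.

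**Step 5. Scale against sampling error.** With 50 patients the exact 95% interval for 25/50 is 35.5% to 64.5%, about 14.5 points either side. In the example, the shift at f = 0.25 (8.75 points) lies within that margin. The shifts at f = 0.5 (17.5 points) and f = 1 (35 points) exceed it. The sample size of 50 has no stated statistical basis (section 5.3), so there is no planned figure to reproduce.

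**The case against.** The best defence is that the operative sections give one sequence. Sections 5.1 and 7.1.1 both enrol and then treat, and the objectives agree. The 2.4.2 sentence is risk/benefit prose. It goes on to pre-operative biopsy, frozen section and adjuvant therapy, so it may describe who is selected for lobectomy. The synopsis wording of inclusion 3 supports reading *receiving* as *to receive*. This is a fair reading and perhaps the intended one. It does not close the point, because the sentence speaks of admission criteria, section 6 contains no such criteria, and section 6 is what a site applies.

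A second defence is that the denominator is open. If only patients who had a lobectomy were counted, the entry point would affect the rate far less. That is true, but such a rate would not measure how feasible conversion is from first diagnosis.

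Four stronger readings are tempting, and the documents do not support them.

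- A reader might infer that the criteria expressly allow prior chemoimmunotherapy. They only fail to exclude it.
- A reader might infer that treatment-naive patients who progress and late-entry responders certainly both count among the 50. Section 8.2 may replace the former: it replaces those who did not receive the study intervention, and section 9.3.1 defines adverse events only from surgery, which suggests that surgery is that intervention.
- A reader might infer that survival is inflated because late entrants have already lived through treatment. Section 9.1 counts 3-year survival from surgery, so everyone so measured has done so, whenever enrolled.
- A reader might infer that entry points differ among the four centers. Nothing in the protocol shows this.

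**Conclusion.** The point holds as an inconsistency about the entry point that the eligibility criteria leave unresolved. Patients already known to have responded can be enrolled without breaking a stated rule, and each such entry biases the R0-lobectomy rate upward for the population named in the objective. The direction rests on two assumptions: that R0 lobectomy is likelier in responders, which the protocol presupposes, and that the denominator is all enrolled patients.

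The size cannot be derived from the documents. The 5.25 to 42 points in the table are illustrations on assumed inputs, and the lower end would be hard to tell from sampling error with 50 patients. No hypothesis test or success threshold depends on the rate, so no formal decision would be reversed. The rate is nevertheless the trial's primary result, and as written it cannot be attributed with confidence to patients assessed at first diagnosis.

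**What to change.** 1. State one enrolment point that fits the objective: consent, eligibility check and enrolment before the first cycle of chemoimmunotherapy.
2. In 6.1 item 3, change *receiving* to *planned to receive*.
3. In 6.2 item 4, add chemotherapy or immunotherapy already started for the present tumor.
4. Reconcile the admission-criteria sentence in 2.4.2 with 5.1, 7.1.1 and section 6. How response should bear on the choice of operation is for the investigators to state.
5. In 9.1, define the primary denominator as all patients so enrolled. In 8.2, do not replace patients who progress or do not reach surgery. Without this step, early enrolment alone would not keep non-responders in the count.

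If late entry must stay, flag it at enrolment and base the primary rate on patients enrolled before therapy. Otherwise, restate the objective as the rate among selected responders.

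The cost is a short amendment and no added procedures. Accrual will be somewhat slower because patients already on treatment no longer qualify, and the rate will probably look less favourable. Without replacement, fewer than 50 patients may contribute to the surgical and postoperative endpoints.
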